One key question that remains to be answered is whether menthol increases the reinforcing effects of nicotine. Pure nicotine, similar to other drugs of abuse, is reinforcing. It is self-administered by cigarette smokers as well as by rodents and primates (Corrigall, 1999; Donny *et al*, 1995; Henningfield *et al*, 1983; Le Foll *et al*, 2007; Sofuoglu *et al*, 2008). However, the primary reinforcing effects of nicotine are less robust compared to other drugs of abuse like cocaine, amphetamines, or opioids. Thus, in addition to nicotine, other stimuli associated with smoking, including the sight, taste, and smell of cigarettes, may also serve as conditioned reinforcers (Sorge *et al*, 2009). Nicotine provides dual-reinforcement. In addition to its primary reinforcing effects, nicotine also enhances the motivational effects of these conditioned reinforcers (Caggiula *et al*, 2009). Thus, if environmental stimuli are intrinsically reinforcing, nicotine self-administration may reflect both the primary reinforcing, and the reinforcement-enhancing, effects of nicotine (Paterson, 2009). Accordingly, if menthol has intrinsic reinforcing properties, then its combination with nicotine may enhance reinforcement. Alternatively, if menthol has no intrinsic reinforcing properties, its combination with nicotine should not enhance reinforcement. To test the validity of these alternatives, carefully controlled studies delivering nicotine and menthol are needed.

Although there are established human laboratory methods to determine drug reinforcement, the study of the relative reinforcing effects of menthol and nicotine present some unique challenges. First, direct comparison of the reinforcing effects of menthol and non-menthol cigarettes in smokers is confounded by the strong conditioning of smokers for either menthol or non-menthol cigarettes. This 'brand loyalty' makes blinding unfeasible in a direct comparison study with smokers. Second, while the local sensory effects of menthol are well recognized, little is known about the behavioral effects of menthol in humans, and how these effects change with menthol dose. Third, it is unclear if menthol is uniquely different than other flavors that have been used in tobacco products. This gap in our knowledge allows tobacco companies to persistently claim that menthol is just a flavor without any behavioral effects of its own (Heck, 2010).

7. Subjects:

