14:00 noon	HR/BP, EKG, M-NWSC, BQSU, SAFTEE

[Type text]

[Type text]

15:00 PM	End of session, collection of urine sample, blood draw Discharge
----------	---

*The same measures will be obtained following saline and each nicotine administration. For brevity, only the measures after saline are shown. Abbreviations: CO: Alveolar carbon monoxide; HR/BP: Heart rate/Blood pressure; EKG: Electrocardiogram; M-NWSC: Minnesota Nicotine Withdrawal Symptom Checklist; BQSU: Brief Questionnaire of Smoking Urges; DEQ: Drug Effects Questionnaire; SAFTEE: Systematic Assessment for Treatment Emergent Events.

12. Data analysis methods

Data analyses: The primary analyses will be intent-to-treat and will include all available data on subjects who complete at least one test day. Mixed-effects models will be used to test the study hypotheses. These models allow for different numbers of observations per subject, use all available data on each subject, and are unaffected by randomly missing data. They also provide flexibility in modeling the correlation structure of the data. All data will be checked for normality and transformations will be applied as necessary. Significance level of 0.05 will be used for the main hypotheses and Bonferroni correction will be applied for post-hoc tests.

Specific Aim #1: To determine if menthol administered via e-cigarettes will change the reinforcing effects of pure nicotine administered intravenously in cigarette smokers who smoke mentholated or non-mentholated cigarettes. The reinforcing drug effects will be measured with the DEQ.

Hypothesis #1A: Concurrent menthol and nicotine administration will lead to greater reinforcement than nicotine and control flavor, saline and menthol, or saline and control flavor conditions.

Hypothesis #1B: Enhancement of nicotine reinforcement by menthol will be greater in menthol smokers than in non-menthol cigarette smokers.

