The main outcome measures will be the “good effects” and “drug liking” items of the DEQ. Mixed effects models will include the within-subject factors nicotine dose (0.25, 0.5 mg nicotine or placebo), menthol dose (low dose of menthol, high dose of menthol, or control flavor) and time of measurement (+1,+3,+5,+10,+15,+30,+45,+55 minutes); the between-subject factor types of cigarette preference (menthol vs. non-menthol) and all possible interactions among these factors. We will also consider order effects for nicotine dose (1, 2 or 3) and session day (1, 2 or 3) and the effects of potential covariates (race, sex, baseline plasma NMR, FTND scores). These effects will be included in the final model if significant. Estradiol and progesterone levels will also be considered as potential covariates in a secondary analysis of women only. We will consider several different correlation structures for the repeated measures within individuals, and will select the best fitting one based on Schwartz Bayesian information criterion. SAS PROC MIXED will be used for the mixed-model analyses.

A significant interaction between nicotine dose and menthol dose, with significantly higher response to menthol + nicotine compared to control flavor + nicotine or control flavor + saline will be considered supportive of hypothesis 1A. A significant interaction between nicotine dose, menthol dose, and group (menthol vs. non-menthol smokers), with significantly stronger effects in menthol smokers than in non-menthol smokers, will be considered supportive of hypothesis 1B. We expect significant effects for both doses and will also test for dose-dependent effects.

[Type text]

[Type text]

Rationale for sample size: Both studies have 80% power to detect large effect sizes ($f=0.4$) for the interactions of interest in repeated measures analysis with 30 subjects per group for a total of 60 subjects at 0.05 significance level. Our preliminary data for both outcome measures show larger magnitude effects for the nicotine effects (all $f>0.5$) and menthol effects are expected to be similarly strong (Sofuoglu et al. 2009a). Applying Bonferroni correction and using an alpha level of 0.01 we have 80% power to detect post-hoc comparisons of medium to large effect size $d'=0.7$ for the menthol and nicotine effects. Our previous study shows larger effects of nicotine $d'>1.0$. To account for up to 70% dropout we will recruit 160 subjects for a target of 60 completers.

13. Risks and benefits

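### The decision rule for hypothesis 1A does not test 1A as worded: it adds an undirected interaction, omits the menthol + saline comparator and joins the other two with *or*

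*Protocol*

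**What the plan says.** Protocol sections 4 and 12 both state hypothesis 1A. Section 12 words it as: "Concurrent menthol and nicotine administration will lead to greater reinforcement than nicotine and control flavor, saline and menthol, or saline and control flavor conditions".

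Later in section 12 comes the only criterion for 1A. It opens with "A significant interaction between nicotine dose and menthol dose, with significantly higher response to menthol + nicotine" and continues "compared to control flavor + nicotine or control flavor + saline will be considered supportive of hypothesis 1A".

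Other statements in section 12 bear on this:
- On alpha: "Significance level of 0.05 will be used for the main hypotheses".
- On outcomes: "The main outcome measures will be the “good effects” and “drug liking” items of the DEQ". How the two items combine into one verdict is not stated.
- The factors in the mixed model are "nicotine dose (0.25, 0.5 mg nicotine or placebo), menthol dose (low dose of menthol, high dose of menthol, or control flavor", plus time and cigarette preference, with all interactions.
- The sample-size paragraph says: "Both studies have 80% power to detect large effect sizes ($f=0.4$) for the interactions of interest in repeated measures analysis with 30 subjects" per group, 60 in total. It expects menthol effects of about the same size as nicotine's.

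The Background, part e), reasons that "if menthol has intrinsic reinforcing properties, then its combination with nicotine may enhance reinforcement".

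**The concern.** 1A is a statement about order: one condition lies above three others. The rule is a statement about effect modification plus two of those three comparisons. A result can satisfy either one without the other.

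At stake is the declared conclusion. Suppose menthol raises ratings by the same amount at every nicotine level and nicotine has its expected effect. Then the combination beats all three comparators, but the rule withholds support from 1A. Conversely, the interaction F test has no direction, so an interaction in which menthol weakens nicotine's effect can count towards support.

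**Working it through.** **1. Hypothesis and rule side by side**

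| Element | Hypothesis 1A | Decision rule |
|---|---|---|
| Above control flavor + nicotine | stated | stated, joined by *or* |
| Above control flavor + saline | stated | stated, joined by *or* |
| Above menthol + saline | stated | absent |
| Nicotine × menthol interaction | absent | required, (3−1)×(3−1) = 4 df, no direction |

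**2. The plan's own power figure.** With f = 0.4 and N = 60, λ = f²N = 0.16 × 60 = 9.6. The noncentral F then gives 78.7% on (2, 116) df, close to the stated 80%; 86.1% on (1, 58) df; and 68.6% on the (4, 232) df of the nicotine × menthol interaction. The repeated-measures form λ = f²Nm/(1−ρ), with m = 3 or 9 measurements, gives over 99% for ρ from 0 to 0.7. The protocol gives neither df nor correlation, so the 80% cannot be tied to one reading. Nothing below depends on it.

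**3. Additive effects.** Let menthol add a > 0 and nicotine add b > 0.
- Control + saline: μ. Menthol + saline: μ + a. Control + nicotine: μ + b. Combination: μ + a + b.
- The combination exceeds these by a + b, b and a, all positive. 1A is true as worded.
- Double difference: (μ + a + b) − (μ + b) − (μ + a) + μ = 0. The interaction null is true.

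A valid test at 0.05 therefore rejects 5% of the time, whatever the sample size or main effects. Per outcome, 1A goes unsupported in at least 1 − 0.05 = 95% of trials.

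**4. Two main outcomes** (correlation assumed between independent and perfect)
- If either item suffices: unsupported in 1 − 0.0975 = 90.25% (independent) to 95% (perfectly correlated).
- If both are required: 95% to 1 − 0.05² = 99.75%.
- Simulated at correlation 0.7, N = 60 and effects of 0.7: 92.3% and 98.7%.

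**5. Simulation of the rule, one outcome.** Assumptions: 3 × 3 within-subject design; equal additive menthol and nicotine effects d, in units of the SD of a pairwise difference (set to 1); 4-df F test at 0.05; pairwise tests at two-sided 0.01, the post-hoc level in the sample-size paragraph; high menthol + high nicotine cell; both named comparisons required; 4,000 trials per row.

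| N | d | Interaction significant | Rule met | All three 1A comparisons significant |
|---|---|---|---|---|
| 60 | 0.5 | 5.0% | 3.7% | 80.3% |
| 60 | 0.7 | 4.7% | 4.4% | 99.2% |
| 60 | 1.0 | 5.4% | 5.4% | 100% |
| 30 | 0.5 | 5.1% | 2.8% | 33.6% |
| 30 | 0.7 | 4.8% | 3.7% | 75.5% |
| 30 | 1.0 | 5.2% | 4.9% | 98.8% |

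The last column depends on the assumed effect and N. The rule's figures stay near or below 5% throughout.

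**6. The other direction.** Take main effects of 1.1 each and an interaction of −0.4. The combination is 1.1 + 1.1 − 0.4 = 1.8, so nicotine adds 1.1 without menthol and 1.8 − 1.1 = 0.7 with it. Menthol weakens nicotine's effect, yet the rule was met in 61% of 2,000 simulated trials (N = 60). The ordering in 1A is still true here. What would be wrong is to read that support as enhancement.

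The *or* opens a further gap if one comparison is enough. Let menthol do nothing alone and take k from nicotine's effect, 0 < k < b. The combination is then k below control + nicotine but b − k above control + saline, with interaction −k. The lenient reading could call 1A supported although it is false.

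**The case against.** The strongest reply is that the interaction is what the trial is about. The Purpose and Specific Aim 1 ask whether menthol alters nicotine's reinforcing effect, 1B speaks of enhancement, and the sample size is set for interactions. Under exact additivity menthol does not modify nicotine's effect, so withholding support answers the aim correctly. This stands. It locates the fault as plausibly in 1A's wording as in the rule, but it does not remove the mismatch, because the protocol offers no other route to support 1A.

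Other points that stand in whole or part:
- The 95% is 1 − alpha under one scenario. A reader might take it as a general failure rate of the test. It is a valid test holding its size when its null is true.
- A reader might infer that the Background predicts additivity. The passage quoted from part e) follows a dual-reinforcement argument in which nicotine strengthens other reinforcers, so it supports a more-than-additive reading at least as well.
- The *or* may mean each comparison, as it naturally does in 1A itself. The text does not settle this.
- The rule speaks of support, which is softer than a requirement.
- Menthol + saline against control flavor + saline is not part of 1A, and listing contrasts is often left to an analysis plan. Its absence is not in itself an error.

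**Conclusion.** The point holds as a mismatch between a stated hypothesis and its stated rule. The rule adds a non-directional 4-df interaction, drops one of three comparators and leaves the link between the other two open. If effects are additive, 1A as worded is true but unsupported about 95% of the time per outcome, and about 90% to nearly 100% over two outcomes. These figures rest only on exact additivity, alpha of 0.05 and the range of correlations in step 4. The success rates for the three comparisons rest on assumed effect sizes.

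A reader might go further and infer that the trial could not tell additive, more-than-additive and null menthol effects apart. The documents do not support that: the factorial model contains the menthol main effect and all interactions, and post-hoc comparisons of menthol effects are planned. The estimates would be sound. The declared conclusion on 1A is what can be wrong.

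**What to change.** Make hypothesis and rule say the same thing, by one of two routes.

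**(a)** As Aim 1 and 1B concern enhancement, reword 1A as more-than-additive enhancement and require the interaction contrast to be in the positive direction.

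**(b)** Keep 1A as worded. Test menthol + nicotine against all three comparators, joined by *and*, each at 0.05, in named dose cells. Because all three must succeed, no Bonferroni correction is needed across comparators. Report the directional interaction as a separate enhancement conclusion and as the base for 1B.

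Under either route, report menthol + saline against control flavor + saline, so that an additive menthol effect is labelled as such, and state how the two DEQ items combine.

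The cost is wording and a few contrasts on data already planned. Route (b) gives two labelled conclusions in place of one. It also lets 1A be met through menthol's own appeal without any change in nicotine's effect, and the report must say so.

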[Type text]
[Type text]

1. Principal Investigator: [name]., Ph.D.

2. Co-Investigators (including VA and WOC staff): While all research staff is trained to provide informed consent, those identified with an asterisk (*) will provide informed consent for this study.

Co-Investigators: [name], Psy.D., [name]., *[name].

[name]. [name].

Nursing Staff: *[name], R.N., [name], R.N., [name] R.N., [name], R.N.

Research Staff: *[name], BSW, *[name], B.S., *[name], CATS, *[name], and *[name], *[name], M.A., [name], M.S.

3. Title of the project

Menthol's Effects on Nicotine Reinforcement in Smokers

4. Purpose, hypothesis and key questions

Purpose: To determine if menthol administered by inhalation via electronic cigarettes (e-cigarettes) changes the reinforcing effects of pure nicotine administered intravenously in cigarette smokers who smoke mentholated or non-mentholated cigarettes. The reinforcing drug effects will be measured with the drug effects questionnaire (DEQ).

Hypothesis: Hypothesis #1A: Concurrent menthol and nicotine administration will lead to greater reinforcement than control flavor and nicotine, menthol and saline, or control flavor and saline conditions. Hypothesis #1B: Enhancement of nicotine reinforcement by menthol will be greater in menthol smokers than in non-menthol cigarette smokers.

5-6. Background and Significance:

a) Introduction

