For this menthol / nicotine reinforcement study, the Test Sessions will be conducted after an Adaptation Session is completed where subjects will learn to use the e-cigarette for delivering the menthol or control (tobacco) flavor. A short e-cigarette questionnaire will also be administered during the Adaptation Session. Then, the nicotine Test Sessions will be performed following overnight abstinence from tobacco. Smokers will be assigned a random sequence of three different e-cigarette conditions (low menthol (0.5% or 5 mg/mL) plus tobacco flavor, high dose menthol (3.5% or 35 mg/mL) plus tobacco flavor or tobacco flavor alone for each of the three Test Sessions (a different menthol condition for each session). The concentration of tobacco flavor will be identical across all conditions. The amount of menthol in high dose condition is the same as those found in commercially available mentholated e-cigarette solutions (AmericaneLiquidStore™). The low dose menthol solution contains menthol that is minimally perceptible by smokers and is in the range of e-cigarette solutions targeting smokers with a preference for low menthol impact in the e-cigarette vapor. In each Test Session, smokers will receive a random order of one intravenous delivery of saline, and two intravenous deliveries of nicotine (3.6 mcg/kg and 7 mcg/kg or 0.25 mg/70 kg and 0.5 mg/70kg), just after the menthol or control flavor is delivered via the e-cigarette. The intravenous dose deliveries will be one hour apart to provide sufficient time for the nicotine and menthol effects to wear off. The nicotine infusion sessions will be at least 24 hours apart to minimize carryover nicotine effects. The main outcome measure will be subjective drug effects as measured with the Drug Effects Questionnaire (DEQ). Other outcomes include cardiovascular measures, cognitive performance, and self-report measures of nicotine withdrawal. Cardiovascular measures include heart rate, systolic and diastolic blood pressure. Cognitive performance will be assessed with the Stroop test, mathematical processing test (MPT), and continuous performance test (CPT). Nicotine withdrawal measures will be measured with the Nicotine Withdrawal Symptom Checklist (NWSC) and the Brief Questionnaire on Smoking Urges (BQSU).

B. Dose Finding Study

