- Subjective Drug Effects: 1) Drug Effects Questionnaire (DEQ), adapted from Soria (1996), will be used during the test session to measure acute drug responses including: liking, cooling, irritation, strength, feeling, stimulation, good effects, bad effects, head rush, and want more. Each item is rated on a 100 mm scale, from 'not at all' to 'extremely'.
- Drug Use: Self-reports of cigarette smoking and use of other tobacco products, alcohol and drugs (cocaine, alcohol, opioids, marijuana, and other illicit drugs) will be assessed with Time Line Follow-Back, which has been shown to be a reliable and valid method for monitoring substance use and other outcomes in longitudinal studies (Miller and DelBoca, 1994; Sobell and Sobell, 1992). The Time Line Follow-Back will be administered at intake.
- Adverse events: SAFTEE: In order to monitor adverse events from the study medications, the SAFTEE will be administered before and after each session. The SAFTEE has been used in a number of pharmacotherapy trials (Levine and Schooler, 1986).
- Cognitive Performance: Cognitive performance will be assessed with 3 tests from the ANAM battery (University of Oklahoma): the Stroop test, the mathematical processing test (MPT), and the continuous performance test (CPT). These 3 tests were chosen because of their sensitivity to tobacco withdrawal and nicotine administration (Heishman *et al*, 2010; Mancuso *et al*, 1999; Myers *et al*, 2008).
 - Stroop Test: This test assesses processing speed, selective attention, and interference (Spreen, 1991). It is a computerized version of the classical Stroop Test (Reeves, 2002). The Stroop design consists of one three-minute block of congruent stimuli, and one three-minute block of incongruent stimuli.
 - Mathematical Processing Test (MPT): This test assesses basic computational skills, concentration, and working memory. An arithmetic problem involving three single-digit numbers and two operators is displayed (e.g., "5 - 2 + 3 ="). The subject presses buttons to indicate whether the answer to the problem is less than five or greater than five.
 - Continuous Performance Test (CPT): This test assesses sustained attention, concentration, and working memory. A target character is displayed for memorization. Then, as individual characters are displayed in sequence, the user presses a designated button only when the displayed character is the target letter.

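### The rule for calling hypothesis 1A supported leaves out the menthol + saline comparator that 1A names, so it can be met when nicotine adds nothing to menthol

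*Protocol*

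**What the plan says.** Hypothesis 1A appears twice in the protocol with the same three comparators. Section 4 reads: "Concurrent menthol and nicotine administration will lead to greater reinforcement than control flavor and nicotine, menthol and saline, or control flavor and saline conditions". Section 12 repeats it under Specific Aim #1: "Concurrent menthol and nicotine administration will lead to greater reinforcement than nicotine and control flavor, saline and menthol, or saline and control flavor conditions".

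The decision rule comes later in section 12. It asks for a significant interaction between nicotine dose and menthol dose, with no direction given, "with significantly higher response to menthol + nicotine compared to control flavor + nicotine or control flavor + saline will be considered supportive" of 1A. It names two comparators. Menthol + saline is not among them, and no other part of the protocol requires menthol + nicotine to exceed it.

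The menthol + saline cell is available. Each session delivers saline and both nicotine doses after the vapour, with "a different menthol condition for each session", and the mixed model covers all nine cells.

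**The concern.** The rule does not test the hypothesis it is meant to decide. Menthol + saline is the only comparator that isolates what nicotine contributes once menthol is present. Without it, a high rating for menthol + nicotine may be due to the menthol vapour alone.

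The protocol leaves that possibility open. Section 5-6 e) treats menthol's own effect as undecided: "if menthol has intrinsic reinforcing properties, then its combination with nicotine may enhance reinforcement". The questionnaire covers "acute drug responses including: liking, cooling, irritation, strength" and other items on one form, so subjects rate the drug just after rating or noticing the sensations of the vapour.

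At stake is the trial's leading claim. The pre-stated rule could declare that menthol and nicotine together reinforce more than either alone when nicotine has added nothing to menthol.

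**Working it through.** The plan gives no figure to reproduce for this rule. The check is algebra on the cell means, followed by a simulation for size.

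**Algebra.** Let control + saline (C+S) = a, control + nicotine (C+N) = a + n, menthol + saline (M+S) = a + m, and menthol + nicotine (M+N) = a + m + n + i, where i is the interaction. If nicotine adds nothing on menthol, M+N = M+S, so i = −n. Then:

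- Interaction: i = −n. This is non-zero whenever nicotine works under control flavor, which section 12 expects.
- M+N − C+N = m + i = m − n. This is positive exactly when menthol alone exceeds nicotine alone.
- M+N − C+S = m + n + i = m. This is then positive too.
- M+N − M+S = 0, so 1A is false.

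Every part of the rule holds while the hypothesis fails. This takes the word joining the two comparators as requiring both. If either one suffices, the condition m > n is not needed.

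**Inputs for the simulation.** From section 12: 60 subjects, interaction tested at 0.05, post-hoc comparisons at 0.01 (two-sided assumed). Assumed: C+S = 0, C+N = 1, and a within-session paired-difference SD of 1.4, 1.0 or 0.7. These give a nicotine d' of 1/1.4 = 0.71, 1/1.0 = 1.0 and 1/0.7 = 1.43. The first two match the detectable d' of 0.7 and the bound of 1.0 that the protocol reports from earlier work ("Our previous study shows larger effects of nicotine"); the third lies above that bound. Taking d' as standardised by the paired-difference SD is also an assumption. It is a reasonable one: a paired t-test at 0.01 needs 28 subjects for 80% power at d' = 0.7 and has 85% with 30, while a two-sample test with 30 per group has 52%.

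The simulation used 3 × 3 within-subject cells with the low dose at half the high-dose effect, a 4-df Hotelling test for the interaction, and paired t-tests at high menthol with the 0.5 mg dose. It ran 40,000 trials per scenario. Menthol condition is fixed within a session, so a second set of runs adds a session variance equal to the residual variance.

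**Rule met although M+N = M+S (%), at SD 1.4 / 1.0 / 0.7:**

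| M+S = M+N | No session variance | With session variance |
|---|---|---|
| 1.0 | 0.2 / 0.4 / 0.6 | – |
| 1.1 | 0.8 / 3.3 / 6.8 | 0.8 / 1.9 / 3.4 |
| 1.25 | 6.2 / 23.8 / 54.5 | 3.3 / 10.4 / 24.8 |
| 1.5 | 42.7 / 87.4 / 99.8 | 18.7 / 52.8 / 89.0 |

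Adding M+N > M+S as a requirement gives at most about 0.5% in every scenario.

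**Hand check of one entry.** At M+S = M+N = 1.25 and SD 1.0, the limiting step is M+N against C+N, a difference of 1.25 − 1 = 0.25. The noncentrality is 0.25 × √60 / 1.0 = 1.94 and the critical t on 59 df is 2.66. The noncentral t gives 24.4% for this step alone, against 23.8% for the whole rule.

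**If either comparison suffices.** Without session variance, false support is about 87 to 100% over the three SDs, even when menthol and nicotine are equal (1.0).

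**The case against.** The strongest reply concerns reach. With both comparisons required, false support needs nicotine to work alone, menthol to beat nicotine, and nicotine to add nothing to menthol. Section 12 expects menthol effects about as strong as nicotine's. At equality the rate is below 1%, and at a 10% menthol advantage it is at most 6.8%. The large figures need a 50% advantage that the protocol does not predict. All this stands, and the percentages should be read with it. It does not make the rule right: the protocol also treats menthol's own effect as unknown, and the less strict reading removes the protection.

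The size also depends on the assumed variability and sample. The SD of 0.7 implies a d' that the protocol does not state. With 30 subjects instead of 60, the 1.25 scenario gives about 0.8 / 5.2 / 22.5%, or 0.6 / 2.5 / 9.9% with session variance. Hypothesis 1A concerns the whole sample, so 60 is the natural number.

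The point about vapour sensations is only suggestive. The main outcomes are the good-effects and liking items; cooling and irritation are separate items outside the rule.

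A positive interaction, together with nicotine not lowering the response under control flavor, would imply M+N > M+S in expectation. That is correct, but the rule asks for no direction.

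Finally, 1A can be true with purely additive effects (C+N = M+S = 1, M+N = 2). The mandatory interaction then lets the rule succeed in only about 5% of trials, with or without M+S. That is a separate limit of the rule, which adding M+S neither causes nor cures. Equality of M+N and M+S would be visible in the results, but a rule fixed in advance should not depend on someone noticing it.

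**Conclusion.** The concern holds. The hypothesis names three comparators and its support rule names two, and the missing one is needed to show that nicotine adds to menthol. This follows from the text and the algebra and needs no assumed effect size.

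The practical size does rest on assumptions. With both named comparisons required and menthol alone equal to nicotine alone, the risk is negligible. It becomes material once menthol alone exceeds nicotine alone by about a quarter: 3.3% to 54.5% across the SDs and session variances examined. At a 50% excess it is 18.7% to 99.8%. Replacing the Hotelling test by a repeated-measures F(4,236) moves the false-support figures by at most 1.6 points. The rule should be corrected; the design and the model can stay.

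**What to change.** Rewrite the rule so that 1A is supported only if the nicotine-by-menthol interaction is significant and menthol + nicotine is significantly higher than each of control + nicotine, menthol + saline and control + saline, at the same menthol and nicotine doses. State the dose pairs and questionnaire items for which this must hold. Within one dose pair and item, requiring all three comparisons together needs no further split of alpha. Across pairs and items the existing Bonferroni provision stays.

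Separately, as a limit on interpretation and not as part of the criterion, report the sign of (M+N − C+N) − (M+S − C+S), and speak of enhancement of nicotine's effect only if it is positive.

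The cost is one sentence, with the same data and model. Power at SD 1.4 / 1.0 / 0.7, without session variance:

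| True situation | Two comparators (%) | Three comparators (%) |
|---|---|---|
| Enhancement, no menthol effect of its own (C+N 0.5, M+S 0, M+N 1.0) | 22.8 / 51.2 / 87.0 | 22.8 / 51.2 / 87.0 |
| Enhancement with a menthol effect (C+N 0.5, M+S 0.5, M+N 1.5) | 28.4 / 53.2 / 86.8 | 28.4 / 53.2 / 86.8 |
| 1A true but sub-additive (C+N 1, M+S 1, M+N 1.5) | 8.0 / 42.7 / 86.6 | 3.5 / 35.9 / 86.4 |

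The loss is confined to the sub-additive case. With session variance that row becomes 3.5 / 21.9 / 75.9 against 1.6 / 18.9 / 75.7.
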